5.2. General Methods

As described in [Section 3.4](#), in this study ‘**treatment group**’ refers to one of the following:

- Dose Level -1: PF-05082566 1.2 mg/kg q4wks + mogamulizumab 0.5 mg/kg;
- Dose Level 1: PF-05082566 1.2 mg/kg q4wks + mogamulizumab 1 mg/kg;
- Dose Level 1a: PF-05082566 100 mg q4wks + mogamulizumab 1 mg/kg;
- Dose Level 2: PF-05082566 2.4 mg/kg q4wks + mogamulizumab 1 mg/kg;
- Dose Level 3: PF-05082566 5 mg/kg q4wks + mogamulizumab 1 mg/kg.

Baseline characteristics, disposition and efficacy data will be summarized based on the FAS by treatment group.

DLTs will be summarized based on the DLT-evaluable set by treatment group.

Other safety data, exposure data, concomitant medications and non-drug treatments will be summarized based on the safety analysis set by treatment group.

PK data will be summarized based on the PK analysis sets by treatment group.

CCI

Immunogenicity data will be summarized based on the immunogenicity analysis set by treatment group.

5.2.1. Data Handling After the Cut-off Date

Data after the cut-off date may not undergo the cleaning process and will not be displayed in any listings or used for summary statistics, statistical analyses or imputations.

5.2.2. Pooling of Centers

In order to provide overall estimates of treatment effects, data will be pooled across centers. The 'center' factor will not be considered in statistical models or for subgroup analyses due to the high number of participating centers in contrast to the anticipated small number of patients treated at each center.

5.2.3. Presentation of Continuous and Qualitative Variables

Continuous variables will be summarized using descriptive statistics ie, number of non-missing values, mean, median, standard deviation (SD), minimum, maximum and first and third quartile (Q1 and Q3).

Qualitative variables will be summarized by frequency counts and percentages. Unless otherwise specified, the calculation of proportions will include the missing category. Therefore counts of missing observations will be included in the denominator and presented as a separate category.

In case the analysis refers only to certain visits, percentages will be based on the number of patients still present in the study at that visit, unless otherwise specified.

5.2.4. Definition of Study Day

Start day of study treatment is the day of the first dose of study treatment.

The study day for assessments occurring on or after the start of study treatment (eg, adverse event onset, tumor measurement) will be calculated as:

Study day = Date of the assessment/event - start of study treatment +1.

The study day for assessments occurring prior to the first dose of study treatment (eg, baseline characteristics, medical history) will be negative and calculated as:

Study day = Date of the assessment/event - start of study treatment.

The study day will be displayed in all relevant data listings.

5.2.5. Definition of Start of New Anti-cancer Drug Therapy

Start date of new anti-cancer drug therapy is used to determine the end of the on-treatment period (see [Section 5.2.7](#)).

The start date of new anti-cancer drug therapy is the earliest start date of anti-cancer drug therapy recorded in the 'Follow-up Systemic Therapy – for Cancer' eCRF pages that is after the first dose of study treatment. When start date of anti-cancer drug therapy is missing or partially missing, the imputation rules described in [Section 5.3.3.4](#) should be applied using only data from the 'Follow-up Systemic Therapy – for Cancer' eCRF pages.

5.2.6. Definition of Start of New Anti-cancer Therapy

Start date of new anti-cancer therapy (drug, radiation, surgery) is used for censoring in efficacy analyses (see [Section 6.2.2](#)).

The start date of new anti-cancer therapy is the earliest date after the first dose of study treatment amongst the following:

- Start date of anti-cancer drug therapy recorded in the ‘Follow-up Systemic Therapy – for Cancer’ eCRF pages.
- Start date of radiation therapy as identified by clinical review based on data recorded in the ‘Concomitant Radiation Therapy’ eCRF page. The following cases will not be considered as new anti-cancer therapy: ‘Type of Radiation Therapy’ = ‘Palliative’ and radiotherapy to a non-target tumor lesion.
- Surgery date recorded in ‘Concomitant Surgery’ when “Surgery Outcome” = ‘Resected’ or ‘Partially Resected’.

When start date of anti-cancer therapy is missing or partially missing, the imputation rules described in [Section 5.3.3.4](#) should be applied.

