4.1. Inclusion Criteria

Patients must meet all of the following inclusion criteria to be eligible for enrollment into the study:

1. Histological or cytological diagnosis of advanced/metastatic solid tumor malignancy. Dose Finding Cohorts: Tumor types will be limited to CRC, SCCHN, squamous NSCLC, bladder, or ovarian carcinomas which have progressed on standard therapy, or for which no standard therapy is available. Expansion Cohorts: Tumor types may include: Histological or cytological diagnosis of either advanced/metastatic CRC, bladder, ovarian, squamous esophageal, SCCHN, or squamous NSCLC. **NOTE:** Final determination of tumor types for expansion will be made based on emerging data from the dose-finding portion of the study or obtained from ongoing studies testing PF-05082566.
2. Measurable disease by RECIST version 1.1.
3. For Expansion Cohorts only: patients must have tumor accessible for biopsies (core needle biopsy or excision preferred). See [Section 3.1.7](#).
4. Age ≥ 18 years.
5. Eastern Cooperative Oncology Group (ECOG) performance status of 0 or 1.
6. Adequate bone marrow function, defined as follows:
 - absolute neutrophil count (ANC) $\geq 1.5 \times 10^9/L$ ($\geq 1,500/\mu L$);

- platelet (PLT) count $\geq 75 \times 10^9/L$ ($\geq 75,000/\mu L$);
- hemoglobin (Hb) $\geq 9.0 \text{ g/dL}$ ($\geq 5.6 \text{ mmol/L}$).

Patients must be transfusion independent (ie, no blood product transfusions for a period of at least 14 days prior to study registration).

7. Adequate renal function, including:

- serum creatinine $\leq 1.5 \times$ upper limit of normal (ULN); **OR**
- estimated creatinine clearance $\geq 60 \text{ mL/min}$ as calculated using the method standard for the institution.

8. Adequate liver function, including:

- Total serum bilirubin $\leq 1.5 \times$ ULN (unless the patient has documented Gilbert syndrome);
- Aspartate and Alanine aminotransferase (AST & ALT) $\leq 2.5 \times$ ULN;
- Alkaline phosphatase $\leq 2.5 \times$ ULN; ($\leq 5 \times$ ULN in case of bone metastasis).

9. Resolved acute effects of any prior therapy to baseline severity or CTCAE Grade ≤ 1 except for AEs not constituting a safety risk by investigator judgment.

10. Serum/urine pregnancy test (for females of childbearing potential) negative at screening and before the patient will receive the study treatment.

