7.2. Tumor Assessments

Tumor assessments will include all known or suspected disease sites. Imaging may include chest, abdomen and pelvis computed tomography (CT) or magnetic resonance imaging (MRI) scans; brain CT or MRI scan for patients with known or suspected brain metastases; bone scan and/or bone X-rays for patients with known or suspected bone metastases.

The same imaging technique used to characterize each identified and reported lesion at baseline will be employed in the following tumor assessments.

Anti-tumor activity will be assessed through radiological tumor assessments conducted at baseline, and on treatment every 8 weeks \pm 7 days starting from Cycle 1 Day 1 up to 1 year, then every 3 months (\pm 7 days) as specified in [Table 1](#). Timing should follow calendar days starting from C1D1 and should not be adjusted for treatment delays.

Follow up bone scans are required every 16 weeks (\pm 7 days) only if bone metastases are present at baseline and bone scan is used to follow bone lesions on treatment. Otherwise bone imaging is required only if new bone metastasis are suspected and at the time of confirmation of complete response for patients who have bone metastases at baseline. The same imaging technique used at baseline for bone lesions assessments should be used to assess the on treatment response to bones.

In addition, radiological tumor assessments will also be conducted whenever disease progression is suspected (eg, symptomatic deterioration), and at the time of EOT (if not done in the previous 8 weeks).

Note that a lesion biopsied while on study, or a lesion that is irradiated during the study should no longer count as a target lesion.

Assessment of response will be made using RECIST version 1.1 ([Appendix 2](#)) and also by irRC ([Appendix 3](#)).

If radiologic imaging shows progressive disease, tumor assessment should be repeated \geq 4 weeks later in order to confirm progressive disease with the option of continuing treatment per [Section 5.4.5](#) while awaiting radiologic confirmation of progression.

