6.2.2.1. Objective Response as Assessed by the Investigator per RECIST v1.1

The following analyses will be based on the FAS by treatment group. Assessment of response will be made using RECIST v1.1.

Best Overall Response (BOR) will be assessed based on reported overall lesion responses at different evaluation time points from the first dose of study treatment until the first documentation of PD, according to the following rules:

- CR = at least two determinations of CR at least 4 weeks apart and before first documentation of PD.
- PR = at least two determinations of PR or better at least 4 weeks apart and before first documentation of PD (and not qualifying for a CR).
- SD (applicable only to patients with measurable disease at baseline) = at least one SD assessment (or better) ≥ 6 weeks after the first dose of study treatment and before first documentation of PD (and not qualifying for CR or PR).
- Non-CR/non-PD (applicable only to patients with non-measurable disease at baseline) = at least one non-CR/non-PD assessment (or better) ≥ 6 weeks after the first dose of study treatment and before first documentation of PD (and not qualifying for CR or PR).

- PD = progression \leq 12 weeks after the first dose of study treatment (and not qualifying for CR, PR, SD or non-CR/non-PD).
- NE: all other cases.

Only tumor assessments performed on or before the start of any further anti-cancer therapies will be considered in the assessment of BOR. Clinical deterioration will not be considered as documentation of disease progression.

Objective Response (OR) is defined as BOR of CR or PR according to RECIST v1.1

Patients who do not have a post-baseline radiographic tumor assessment (including due to early clinical progression), who receive anti-cancer therapies other than the study treatments prior to reaching a CR or PR, or who die, progress, or drop out for any reason prior to reaching a CR or PR will be counted as non-responders in the assessment of OR. Each patient will have an objective response status (0: no OR; 1: OR). OR rate (ORR) is the proportion of patients with OR in the analysis set.

ORR by treatment group will also be calculated along with the 2-sided 95% CI using the Clopper-Pearson method (exact CI for a binomial proportion as computed by default by the FREQ procedure using the EXACT option).

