In addition, the frequency (number and percentage) of patients with BOR of CR, PR, SD, non-CR/non-PD (applicable only to patients with non-measurable disease at baseline), PD and NE will be tabulated. Patients with BOR of NE will be summarized by reason for having NE status. The following reasons will be used:

- Inadequate baseline assessment (includes missing assessment or non-measurable disease at baseline).
- No post-baseline assessments due to death.
- No post-baseline assessments due to other reasons.
- All post-baseline assessments have overall response NE.
- New anti-cancer therapy started before first post-baseline assessment.
- SD of insufficient duration (<6 weeks after the first dose of study treatment).
- PD too late (>12 weeks after the first dose of study treatment).

Special and rare cases where BOR is NE due to both early SD and late PD will be classified as 'SD too early'.

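### SAP 5.2.6 can count an excisional tumour biopsy as new anti-cancer therapy, because its surgery bullet lacks the clinical review applied to radiotherapy

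*SAP*

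**What the plan says.** SAP 5.2.6 defines a start date for new anti-cancer therapy that "is used for censoring in efficacy analyses". The definition reads: "The start date of new anti-cancer therapy is the earliest date after the first dose of study treatment amongst the following". Three sources follow:

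- **Drug therapy:** the follow-up systemic therapy pages.
- **Radiotherapy:** "Start date of radiation therapy as identified by clinical review based on data recorded in the" radiation page. Palliative radiotherapy and radiotherapy to a non-target lesion are excluded.
- **Surgery:** "Surgery date recorded in ‘Concomitant Surgery’ when “Surgery Outcome” = ‘Resected’ or ‘Partially Resected". There is no review step and no exclusion.

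The date then acts in several places. For response, SAP 6.2.2.1 states: "Only tumor assessments performed on or before the start of any further anti-cancer therapies will be considered in the assessment of BOR". It also lists "New anti-cancer therapy started before first post-baseline assessment" as a reason for a BOR of NE. SAP 6.2.2.2 leaves later scans out of the maximum reduction in target lesions. SAP 6.2.2.5 and Table 3 censor PFS at the last adequate scan before the date, and SAP 6.2.2.3 applies the same rules to DR.

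On biopsies, protocol criterion 3 (section 4.1) says that in the expansion cohorts "patients must have tumor accessible for biopsies (core needle biopsy or excision preferred"). Protocol 7.2 adds: "Note that a lesion biopsied while on study, or a lesion that is irradiated during the study should no longer count as a target lesion".

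**The concern.** The surgery bullet identifies therapy by an outcome code alone. An excision done to obtain tissue, if coded as a resection, meets the definition just as a therapeutic resection does. The neighbouring radiotherapy bullet shows that the authors saw the need to separate treatment that should stop follow-up from treatment that should not, but they did this for radiation only.

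At stake are BOR, objective response and maximum tumour reduction, and also PFS and DR, which the SAP limits to the expansion cohorts. Those are the cohorts for which the protocol names excision as a biopsy method. A patient still on study drug and still being scanned could lose a later confirmation of response or a later documented progression because of a diagnostic procedure.

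**Working it through.** The plan states no figure on this point, so there is none to reproduce. The check applies its rules to one hypothetical patient.

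**Inputs.** Scans every 8 weeks (SAP 6.2.2.5), first dose on day 1, so scans on days 57, 113 and 169. Assumed results: PR, PR, PD. Assumed excision dates: day 43, 71 or 127, recorded on Concomitant Surgery as Resected.

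**Formulas (SAP 6.2.2.3 and 6.2.2.5).** PFS in months = (event or censoring date − first dose + 1) / 30.4375. DR in months = (event or censoring date − first response date + 1) / 30.4375.

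**Step 1: the lesion is not a target lesion, or the remaining lesions stay evaluable.** Table 11 in protocol Appendix 2 still gives PR when target status is PR and non-target status is indeterminate or missing.

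| Excision | BOR / response | PFS (months) | DR (months) |
|---|---|---|---|
| Not counted as therapy | PR / yes | event, 169/30.4375 = 5.55 | event, 113/30.4375 = 3.71 |
| Day 43, before any scan | NE / no | censored at first dose, 1/30.4375 = 0.03 | none |
| Day 71, after an unconfirmed PR | SD / no | censored, 57/30.4375 = 1.87 | none |
| Day 127, after a confirmed PR | PR / yes | censored, 113/30.4375 = 3.71 | censored, 57/30.4375 = 1.87 |
| After PD on day 169 | PR / yes | event, 5.55 | event, 3.71 |

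**Step 2: the lesion is a target lesion and Appendix 2 is read strictly.** Appendix 2 makes target status Indeterminate when a target lesion has been excised, unless progression is documented. The scans after excision are then inadequate under SAP 5.2.11 until PD.

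- **Day 43:** days 57 and 113 are Indeterminate. PD on day 169 is (169 − 1)/7 = 24 weeks after first dose, beyond the 12-week limit for a BOR of PD, so BOR is NE. It also follows two inadequate assessments, so Table 3 censors PFS at first dose. SAP 5.2.6 makes no difference.
- **Day 71:** BOR is SD with or without 5.2.6. Only one inadequate scan precedes PD, so Table 3 would count an event at 5.55 months; 5.2.6 turns this into censoring at 1.87.
- **Day 127:** the confirmed PR stands either way. The PFS event at 5.55 becomes censored at 3.71, and the DR event at 3.71 becomes censored at 1.87.

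So when a target lesion is excised, what 5.2.6 removes by itself is mainly the later progression event. When other lesions remain evaluable, it can also remove the response.

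**Scale.** One responder lost among n patients lowers ORR by 1/n. At the expansion maximum of 40 this is 1/40 = 2.5 percentage points. The documents do not say how many such patients to expect.

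**The case against.** The strongest objection is that Concomitant Surgery looks like a page for cancer surgery. SAP 6.5.5 names it as a source for the listing of anti-cancer treatment. SAP 6.5.1.4 treats its counterpart, Prior Surgery, as a source of prior anti-cancer therapies. SAP 6.5.4 takes concurrent procedures from a different page. This largely disposes of a reading that a reader might be tempted to make, that any unrelated operation ends follow-up. An appendectomy is a poor example in any case, since protocol 8.7 has it recorded as treatment of the adverse event.

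The page argument does not dispose of the biopsy case. SAP 6.5.5 names the radiation page in the same way, yet 5.2.6 still filters its records. A page for cancer surgery can also hold a tumour excision done for diagnosis.

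Second, the biopsy effect rests on things that cannot be seen. Biopsy timing is redacted, and neither document says on which page a biopsy is entered or how its outcome is coded. Criterion 3 concerns accessibility of tumour and gives no date, and a biopsy before first dose cannot trigger the rule. One occasion that is visible, in the protocol's document history, is at progression, where RECIST v1.1 results no longer change. All of this stands and makes the point conditional.

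Third, a reader might infer that the SAP contradicts protocol 7.2. That goes too far. Section 7.2 removes a lesion from the target set; it does not promise that the patient stays evaluable, and step 2 shows that Appendix 2 may itself make later non-PD scans unusable.

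Finally, SAP 5.1.1 plans no hypothesis test, protocol 9.4 makes efficacy descriptive, and the primary endpoint, DLT, is untouched. That limits the importance of the point but does not remove it.

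**Conclusion.** The point holds in conditional form. As written, SAP 5.2.6 would treat an excisional tumour biopsy as new anti-cancer therapy if three conditions are met: it is recorded on Concomitant Surgery, its outcome is Resected or Partially Resected, and it falls after first dose and before documented PD. Later scans are then lost to BOR and maximum reduction, and PFS and DR are censored early. Nothing in the SAP exempts it.

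The effect depends on timing. It is nil for RECIST v1.1 endpoints after documented PD, and responses already confirmed are kept. For some target-lesion excisions Appendix 2 would have produced the same result.

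The figures in the working describe one assumed patient and are not estimates for the trial. Without a frequency of excision, a count of patients lost or a shifted ORR for the whole trial would be invention. This is a small, inexpensive correction to a stated derivation rule.

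**What to change.** Replace the surgery bullet in SAP 5.2.6 with wording such as: surgery identified by clinical review of Concomitant Surgery records (outcome Resected or Partially Resected) as treatment of the malignancy under study; biopsies taken for the study or for diagnosis are not new anti-cancer therapy. It would also help to name the eCRF page on which on-study biopsies are recorded.

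The cost is a sentence or two in the SAP and a brief clinical review of a few surgery records, alongside the review already planned for radiotherapy.

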5.2.7. Definition of On-treatment Period

Safety endpoints will be summarized based on the on-treatment period unless otherwise specified.

On-treatment period is defined as the time from the first dose of study treatment through minimum (30 days + last dose of study treatment, start day of new anti-cancer drug therapy – 1 day).

Safety data collected outside the on-treatment period as described above will be listed and flagged in listings but not summarized.

5.2.8. Standard Derivations and Reporting Conventions

The following conversion factors will be used to convert days into weeks, months or years:
1 week = 7 days, 1 month = 30.4375 days, 1 year = 365.25 days.

Demographics and physical measurements:

- Age [years]:
 - (date of given informed consent - date of birth + 1) / 365.25;
 - In case of missing day, day only: Age [years]: (year/month of given informed consent – year/month of birth);
 - In case only year of birth is given: Age [years]: (year of given informed consent - year of birth).

The integer part of the calculated age will be used for reporting purposes.

- $\text{BMI (kg/m}^2\text{)} = \text{weight (kg)}/[\text{height (m)}]^2$;
- $\text{BSA (m}^2\text{)} = ([\text{height (cm)} \times \text{weight (kg)}] / 3600)^{0.5}$.

For reporting conventions, mean and median should generally be displayed one more decimal place than the raw data and standard deviation should be displayed to two more decimal places than the raw data. Percentages will be reported to one decimal place. The rounding will be performed to closest integer / first decimal using the common mid-point between the two consecutive values. Eg, 5.1 to 5.4 will be rounded to an integer of 5, and 5.5 to 5.9 will be rounded to an integer of 6.

5.2.9. Unscheduled Visits

Generally, data collected at unscheduled visits will be included and analyzed for both safety and efficacy analyses in the same fashion as the data collected at scheduled visits except where otherwise noted in the sections that follow. Descriptive statistics (mean, SD, median, minimum, maximum, quartiles) by nominal visit or time point for safety endpoints such as laboratory measurements, ECGs and vital signs will include only data from scheduled visits.

5.2.10. Adequate Baseline Tumor Assessment

Adequate baseline is defined using the following criteria:

- All baseline assessments must be within 42 days prior to and including the first dose of study treatment.
- All documented lesions must have non-missing assessments (ie, non-missing measurements for target lesions and non-missing lesion status at baseline for non-target lesions).

5.2.11. Adequate Post-baseline Tumor Assessment

An adequate post-baseline assessment is defined as an assessment where a response of CR, PR, SD, non-CR/non-PD, or PD can be determined (see [Section 6.2.2.1](#)). Time points where the response is not evaluable (NE) or no assessment was performed will not be used for determining the censoring date.

5.3. Methods to Manage Missing Data

5.3.1. Missing Data

Unless otherwise specified, all data will be evaluated as observed, and no imputation method for missing values will be used.

In all patient data listings imputed values will be presented. In all listings imputed information will be flagged.

Missing statistics, eg, when they cannot be calculated, should be presented as 'ND' or 'NA'. For example, if N=1, the measure of variability (SD) cannot be computed and should be presented as 'ND' or 'NA'.

